2.2.1 Cardiac Output

Cardiac output will be continuously measured by FloTrac and ClearSight, while cardiac output will be intermittently measured by the Swan-Ganz catheter, using the thermodilution method. During a 5- minute period of thermodilution and cardiac output determination, each subject will be assessed for hemodynamic stability. Should there be any instability, the bolus will be rejected. All data will be recorded and any rejected values will be clearly identified in the eCRF.

The rejection criteria that will be used to determine hemodynamic instability are detailed below:

- FloTrac and ClearSight will display mean arterial pressure (MAP). If MAP varies > 15% during the 30-sec period of each intermittent thermodilution, the bolus will be rejected.
 - i. If more than 1 result is greater than 15% of the mean or the prespecified rejection criteria is met, discard the entire series, and repeat the series of four thermodilutions.
 - Note: The likely cause for 2, 3 or 4 results being greater than 15% of the mean is technique dependent, i.e., shooting the thermodilution either fast, slow or drawing up the incorrect amount of fluid.
 - ii. If none the results are greater than 15% of the mean or the prespecified rejection criteria is not met, discard one result that is furthest from the mean.
- FloTrac and ClearSight will also display Pulse rate. If Pulse varies > 15% during the 30-sec period of each ITD, the bolus will be rejected.
 - i. If more than 1 result is greater than 15% of the mean or the prespecified rejection criteria is met, discard entire series, and repeat the series of four thermodilutions.
 - Note: The likely cause for 2, 3 or 4 results being greater than 15% of the mean is technique dependent, i.e., shooting the thermodilution either fast, slow or drawing up the incorrect amount of fluid.
 - ii. If none the results are greater than 15% of the mean or the prespecified rejection criteria is not met, discard one result that is furthest from the mean.
- ClearSight will display Physiocal. If Physiocal is not at least 30 beats, the bolus will be rejected.

For Cardiac Output comparisons of FloTrac and ClearSight to Swan-Ganz ITD, all hemodynamic monitors will be time aligned.

The CO values from ClearSight and FloTrac for the analyses will be prepared as follows:

Determine the averaging window corresponding with each bolus injection

	Revision Date: De	ecember 2, 2020	Rev	В	For Use Only by Affiliates of Edwards Lifesciences	Page 7
Edwards	Title	Statistical Analysis Pl Nonrandomized, Obso Monitoring in Pediatri	ervatio	onal St		

- Average the CO over the 30 second period
- Determine the average of 3 of 4 CO values

The CO values from Swan-Ganz ITD for analyses will be prepared as follows:

- Determine the CO from each of the 3 of 4 accepted bolus injections
- Determine the average of 3 of 4 CO values

The CO values from Swan-Ganz ITD for analyses will be prepared as follows:

- Determine the CO from each of the 3 of 4 accepted bolus injections
- Determine the average of 3 of 4 CO values

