8. SCHEDULE OF EVENTS & PROCEDURES

Schedule of Events

Lifesciences Corporation.

The following matrix shows the scheduled assessments through the end of the Study (30-Day Follow Up).

Study Procedure / Exam	Subject Screening	Procedure	Discharge	30-Day Follow Up (±14 Days)
Obtain Informed Consent	X	7 10000.010	2.00.10.180	(==: ==;
Perform Inclusion / Exclusion Evaluation	Х			
Obtain Medical History / Subject Demographics ¹	Х			
Assign Subject ID		Х		
Enter Subject Data into Monitor		Х		
Vital Signs		Х		
Monitoring Duration		Х		
Data download from Monitor		Х		
Obtain Fluid and Vasoactive Medication Administration Record ²		Х		
Complete eCRFs	Х	Х	Х	Х
Record Adverse Events, if applicable		Х	Х	Х
Phone Contact 30-day follow up / Mortality Determination				х

The duration of individual study participation is expected to be 30 days (±14 days) after procedure.

Data collection will occur during the study via the HemoSphere platform and electronic case report forms (eCRFs). The 30-day follow-up phone contact will be recorded on the applicable eCRF.

2019-08 Page **26** of **52 CONFIDENTIAL**

¹ Medical History / Subject Demographics / Surgical and Clinician Demographics can be obtained prior to procedure, either at the screening visit or on the day of procedure.

² Can be collected via the hospital record system anytime on the day of procedure or thereafter.

THIS DOCUMENT CONTAINS CONFIDENTIAL AND PROPRIETARY INFORMATION OF EDWARDS LIFESCIENCES, LLC. IT MAY NOT BE REPRODUCED OR DISCLOSED WITHOUT PRIOR WRITTEN PERMISSION FROM EDWARDS LIFESCIENCES, LLC.

Edwards Lifesciences, Edwards, the stylized E logo, HemoSphere, Swan-Ganz, FloTrac, ClearSight and ForeSight Elite are trademarks of Edwards

P(OGO Study	ĺ
St	tudy #2019-08	ì

Intermittent Thermal Dilution Assessment(s)

Using the Swan-Ganz thermodilution pulmonary artery catheter, two series of four (4) intermittent dilutions should be administered by the Investigator while in the cath lab. The dilution curves are analyzed and averaged to give one (1) CO value.

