CO measured by the ClearSight and FloTrac systems will be simultaneously compared with the CO measured by the Swan-Ganz catheter using the thermodilution method. There will be 2 sets of 4 measurements recorded over a 30-second interval, during the Swan-Ganz thermodilution bolus injection. Those 4 measurements will be pair-matched by time in the ClearSight and FloTrac systems. The same number of measurements that will be recorded during the Swan-Ganz thermodilution will be recorded for the ClearSight and FloTrac devices. The following thermodilution procedure will be used:

A 10 ml sample of iced glucose solution (5%) will be drawn through an iced injectate container (CO-SET+ or any other container that meets the requirements, as determined by the investigator) and injected in a steady manner. Four TD CO determinations will output, preferably within 5 minutes. From there, three values, will be averaged to obtain one single value. Each thermodilution curve will be visually checked before acceptance. The dilution curve will be automatically corrected for the temperature of the blood and of the injectate measured at the entrance of the catheter lumen. Values for temperatures will be stored together with the thermodilution values. The entire series of four thermodilution estimates will be rejected if, during an injection, the HemoSphere advanced monitor displays an alert signal, if the injectate temperature is above 10 °C, or when the curve of the dilution is abnormal. In case of rejection, the entire series of four thermodilutions will be repeated.

Hemodynamics and respiratory rate must be stable during the TD series, since variability violates the assumption of stability that is required for the TD technique. Sponsor-instream review of the TD series will occur after each catheterization to determine if hemodynamic variability occurred and the site team will be retrained on the importance of conducting the TD technique during hemodynamic stability.

Clinical Study Completion or Early Termination

The IRB will be notified upon completion or premature termination of the study. Edwards retains the right to suspend or prematurely terminate this clinical study at any time.

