- Pain associated with inflation of the cuff
- Slight numbness of the fingertip

Below is a list of anticipated risks that may be associated with the use of ForeSight Elite Sensors:

- Allergic reaction to adhesive on sensors
- Skin irritation

POGO Study	
Study #2019-08	

Risk Management

The study devices have been tested to an established regimen of safety and performance testing and, with the exception of the ClearSight Module used in the HemoSphere platform, have been cleared by the US FDA in adults. The ClearSight technology has been cleared for use in adults with the EV1000 Monitor; however, it has not been cleared for use with the HemoSphere advanced monitoring platform.

The current risks identified for using these products do not outweigh the benefit the patient will receive. Furthermore, this study is:

- 1) Being conducted on patients who are already planned to receive an arterial line and a Swan Ganz catheter and the addition of FloTrac and ClearSight do not add to the invasiveness of the study,
- 2) Being conducted on patients who are already planned to receive thermodilutions
- 3) An observational study as opposed to an interventional study
- 4) Not relying on the data obtained from the FloTrac and ClearSight to treat patients

Collecting data does not introduce any new risks in relation to these products. Regarding the ClearSight Module used in the HemoSphere platform, thorough testing has been performed to show that this system functions as intended. As such collectively, the risks do not outweigh the benefits.

Benefits

There are no guaranteed benefits from a subject's participation in this study. However, the ForeSight Elite Sensors are cleared for pediatric use and provide the benefit of continually monitoring oxygen saturation of tissue with accuracy and precision. When desaturation of tissue occurs, the following may occur:

- Cognitive disfunction
- Extended time on mechanical ventilation
- Extra days spent in the hospital or intensive care unit (ICU)
- Increased post-operative nausea and vomiting

POGO Study]
Study #2019-08	

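### Thermodilution curves are accepted by eye, and nothing in the plan hides the FloTrac and ClearSight cardiac output from the person accepting them

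*Combined protocol and SAP*

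**What the plan says.** Protocol section 8 (Intermittent Thermal Dilution Assessment(s)) states that "two series of four (4) intermittent dilutions should be administered by the Investigator while in the cath lab". On acceptance it says "Each thermodilution curve will be visually checked before acceptance". It does not say who makes the check or against what criteria.

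The grounds for rejecting a series are a monitor alert, an injectate temperature above 10 °C, or "when the curve of the dilution is abnormal". The first two are objective; the third is not defined. The consequence is that "In case of rejection, the entire series of four thermodilutions will be repeated". No limit on repeats is given.

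SAP 2.2.1 adds stability rules (MAP or pulse rate varying by more than 15%, Physiocal below 30 beats). It says "Cardiac output will be continuously measured by FloTrac and ClearSight" during this period and "FloTrac and ClearSight will display mean arterial pressure (MAP", with matching statements for pulse rate and Physiocal. If the series stands, the one result furthest from its own series mean is discarded and the other three are averaged.

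Two statements come near to masking. Protocol section 9 (Risk Management) describes the study as "Not relying on the data obtained from the FloTrac and ClearSight to treat patients". SAP 2.2 says device values are matched to the thermodilution times retrospectively. The first concerns treatment, and the second concerns data assembly after the case. Neither says what the operator may see during a series.

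**The concern.** In a method-comparison study the reference should be obtained without knowledge of the reading under test. Here the discretionary step, the judgement that a curve is abnormal, is taken at the bedside while both test devices are running, and one such call replaces the whole reference value. An operator who can see the test CO may, without intending to, look harder at curves whose result disagrees with it.

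If that happened, mean bias would shrink toward zero and the differences would spread less. Both changes favour the device: the first helps the equivalence test on bias, and the second narrows the limits of agreement and lowers percent error. The analysis set contains only values that were not rejected (SAP 4 and 5.2), so the primary test would use the selected readings.

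**Working it through.** **Text check.** I looked in both documents for any statement that test-device CO is hidden, or that curves are read by someone masked to it. There is none. I also found no statement that CO is on the screen. Its visibility is inferred from three facts: the devices measure CO live, their displays are used in the rejection rules, and no masking is specified. SAP 6.3 describes the MAP, pulse and Physiocal checks as made after download. It also has the clinician repeat an unstable series, which can only be done in the cath lab, so some of the judgement is made live.

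**Inputs.**
- Margin 0.5 L/min, alpha 0.025 per comparison and n = 60 (SAP 2.3.1). The plan's inflation reproduces: 60 / (0.655 × 0.90) = 101.8, i.e. 102.
- Total variance 1 and ICC 0.94 to 0.98 (SAP 2.3.1). Bolus SD = √(1 − ICC), giving √0.02 = 0.141 and √0.06 = 0.245 L/min.
- A larger bolus SD as an assumption: the ±20% thermodilution precision quoted in SAP 2.3.2, read as 2 SD at an assumed CO of 5 L/min, gives 0.20 × 5 / 2 = 0.5 L/min. With between-subject SD 0.99 this implies ICC = 0.9801 / (0.9801 + 0.25) = 0.80, outside the plan's range.

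**Model.** Each subject has a true test-minus-reference difference drawn from N(0.5, 0.99²), so mean bias is exactly at the margin. There are two series of four boluses. In each, the bolus furthest from its own series mean is dropped and three are averaged, as SAP 2.2.1 prescribes. The two series are averaged within subject, and the two one-sided t-tests are run on 60 subjects.

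- *No steering:* every first series is kept.
- *Steering:* a series is repeated once, and the repeat kept, whenever its error moved the reference away from the test value. By symmetry this is about half of all series.

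**Results.** Observed bias, SD of subject-level differences, and half-width 1.96 × SD, in L/min:

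| Bolus SD (ICC) | Bias, steered | SD, unsteered → steered | Half-width, unsteered → steered | False-pass rate, steered |
|---|---|---|---|---|
| 0.141 (0.98) | 0.487 | 0.991 → 0.965 | 1.94 → 1.89 | 0.032–0.035 |
| 0.245 (0.94) | 0.475 | 0.998 → 0.951 | 1.96 → 1.86 | 0.041–0.042 |
| 0.5 (0.80, assumed) | 0.448 | 1.016 → 0.925 | 1.99 → 1.81 | 0.063–0.071 |

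The ranges in the last column are simulation error across repeated runs. Without steering the rate stays at about 0.025, so the written discard rule does no harm by itself. If only half of the adverse series are repeated, the rates are about 0.029, 0.030 and 0.040.

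**How far the planned secondary analyses would show it.** Under full steering, using every recorded bolus (rejected ones included) gives about 0.026 to 0.032. Using first-attempt series only gives 0.024 to 0.026.

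**The case against.** The case against is substantial, and most of it stands.

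- **Most rejection grounds are objective.** MAP, pulse, Physiocal, injectate temperature and monitor alert leave little room. Only the visual check and the undefined abnormal curve are open.
- **The operator does not choose which bolus to drop.** A reader might infer that the single bolus furthest from the test reading can be discarded, which would bias the result more. The documents do not allow it: SAP 2.2.1 drops the one furthest from its own series mean, and protocol section 8 repeats the whole series.
- **The damage is not irrecoverable.** A reader might infer that no later analysis could correct it. But rejected values are recorded in the eCRF (SAP 2.2.1), SAP 3.1.2 compares bias intervals with and without rejected data, and SAP 6.3 analyses all recorded values. The SAP 6.3 analysis is labelled exploratory, and neither replaces the primary test.
- **The sponsor's reviewer does not accept curves.** The protocol says "Sponsor-instream review of the TD series will occur after each catheterization to determine if hemodynamic variability occurred", followed by retraining of the site. It gives that reviewer no part in acceptance.
- **An effect on both comparisons is not shown.** There are two test devices and one reference. If their readings lie on opposite sides of it, moving the reference toward one moves it away from the other. The simulation has a single test value.

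The objection does not remove the gap itself: an open-ended visual judgement is made on the reference while the test devices run, and nothing masks their CO.

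**Conclusion.** The point holds as a low-cost improvement to the design, not as evidence of bias. At the plan's own ICC the effect is modest even with an operator who repeats every adverse series: bias falls by 0.013 to 0.025 L/min (0.500 − 0.487 and 0.500 − 0.475), and the false-pass rate goes from 0.025 to about 0.033–0.041. The figure of about 0.066 needs a bolus SD of 0.5 L/min, which the plan's ICC does not support.

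These figures assume true bias exactly at the margin, 60 analysable subjects and one repeat per series. The modelled operator reacts to the reference error itself; a real one would see only the gap between the two readings. The scenario is therefore close to an upper bound for a single repeat, although the plan states no cap on repeats. It rests on the inference that CO is visible, which the sponsor can confirm or rule out.

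**What to change.** In protocol section 8 and SAP 2.2.1, state that during each thermodilution series only MAP, pulse rate and Physiocal are shown from FloTrac and ClearSight. State also that their CO, CI and SV are hidden from the person accepting the curves. If the displays are already set up this way, one sentence saying so is enough.

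As a check, add to the SAP a table of test-minus-reference differences in accepted and in rejected series, by device. The values are already recorded, so no new data are needed.

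The cost is a display setting, brief site training and one table. Sample size does not change. The drawback is that operators will not see the investigational CO during the series; the protocol already says those data are not relied on for treatment.

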The sample size calculation for this hypothesis is based on the one-sample t-test for equivalence. The desired outcome is to reject the null hypothesis at the 0.025 significance level. For this equivalence test of bias, two comparisons will be performed: FloTrac vs Swan-Ganz and ClearSight vs Swan-Ganz. In order to preserve the overall type 1 error rate at 0.05, the Bonferroni Correction will be used to adjust for multiple comparisons. Assuming a true mean bias of 0.0 and a SD of 1.0 l/min in the cardiac output, the sample size required for δ =0.5, alpha=0.025, and power=90% to reject the null hypothesis is 45, ignoring the ICC. After considering ICC for eight repeated measures (m=8), adjusting for multiple comparisons, considering comparisons of between two target devices and a reference device pairs, simultaneously, a sample size of 60 Subjects is needed. After considering a 34.5% rejection rate for hemodynamic instability, 10% lost to follow-up rate, and 6 roll-in Subjects for the learning curve, up to 108 (102) evaluable Pivotal Subjects and 6 Roll-in Subjects) will be enrolled into the study.

By simulating the study results with a mixed effect model, using repeated measurement data collected from a similar study, although the sample size estimate from this approach is conservative, it is reasonable and rational.

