6.3 Handling of Invalid Data

After downloading the data from the hemodynamic monitors, abnormal observations will be checked and evaluated for hemodynamic stability. Should there be any instability, the result will be rejected. All data will be recorded, and any rejected values will be clearly identified in the eCRF.

The rejection criteria that will be used to determine - hemodynamic instability are detailed below:

- Mean arterial pressure (MAP): If MAP varies > 15% during the 30-sec period of each intermittent thermodilution, the bolus will be rejected.
- Pulse rate: If Pulse varies > 15% during the 30-sec period of each ITD, the bolus will be rejected.
- PhysioCal: If PhysioCal is not at least 30 beats, the bolus will be rejected.

•

Upon taking four (4) thermodilution measurements and given the above criteria for classifying data as invalid, Edwards proposes to remove the one measurement that is the greatest outlier of the four. If upon the rare occasion two or more outliers measure greater than 15% from the mean, within a series of measurements, or hemodynamic instability results when these observations are taken, the clinician will repeat the series. If this scenario of repeating the series is missed by the clinican during the clinical procedure and discovered by the statisticians during data review, the outliers will be analyzed separately. In addition to the results for the collected parameters, the number of subjects with less than 3 and number of subjects with at least 3 valid values, and results of subjects will be tabulated separately, and reported. Those subjects who have less than 3 valid measurements and were missed for repeated testing by the clinician performing the thermodilutions will be considered as protocol deviations or protocol violations.

Additionally, a supplementary exploratory analysis will be reported using all the recorded values (valid and invalid) to assess the impact of the excluded values.

[figure not shown]

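### A Physiocal value that only ClearSight displays rejects the whole bolus, so as written it also removes the matched FloTrac pair from the primary and secondary tests

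*Combined protocol and SAP*

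**What the plan says.** SAP 2.2.1 lists three criteria for hemodynamic instability. Each rejects a bolus.

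- **MAP:** "FloTrac and ClearSight will display mean arterial pressure (MAP). If MAP varies > 15% during the 30-sec period".
- **Pulse:** the same 15% limit, applied to the rate that both devices show.
- **Physiocal:** "ClearSight will display Physiocal. If Physiocal is not at least 30 beats, the bolus will be rejected".

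SAP 6.3 repeats all three, the last as "PhysioCal: If PhysioCal is not at least 30 beats, the bolus will be rejected". Neither section says that a Physiocal rejection affects only the ClearSight pair. Neither says which device governs if the two disagree on MAP or pulse.

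SAP 3 uses the evaluable set for the primary and secondary endpoints, and SAP 5.2 limits that set to subjects with non-rejected CO pairs. SAP 4 describes one analysis set across all systems. SAP 2.3.1 and SAP 3 nevertheless test FloTrac versus Swan-Ganz and ClearSight versus Swan-Ganz as two comparisons, with a Bonferroni correction.

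The excluded data are not discarded. SAP 2.2.1 records all values and flags the rejected ones. SAP 3.1.2 and 3.4.1 plan bootstrap intervals for bias and percent error that also cover rejected data. SAP 6.3 adds that "a supplementary exploratory analysis will be reported using all the recorded values (valid and invalid) to assess the impact of the excluded values".

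**The concern.** FloTrac and ClearSight each have their own comparison with thermodilution and their own test. A FloTrac pair should be excluded when the thermodilution, the patient's stability or the FloTrac reading is in doubt. Physiocal, on the documents' own description, is shown by ClearSight alone. When it falls below 30 beats, the FloTrac reading and the thermodilution for that bolus may both be sound, yet the bolus goes and the FloTrac pair with it.

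Two things are at stake. FloTrac loses data for a reason tied to the other device, so its estimate is less precise and rests on boluses selected by ClearSight. In addition, every rejection falls under the single label of hemodynamic instability, so a reader of the results could not tell patient instability from a ClearSight-only exclusion.

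The MAP and pulse rules have a related gap. Both devices display these signals, and the plan does not name the one that decides.

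**Working it through.** **1. Scope of the rule.** SAP 2.2.1 and 6.3 agree: the source is ClearSight, the unit rejected is the bolus, and no comparison is named. SAP 3 and 5.2 then take non-rejected pairs into both confirmatory tests. The loss of FloTrac pairs therefore follows from the rules as stated. The protocol's thermodilution section (section 8) has its own grounds for rejection: a monitor alert, injectate temperature above 10 °C, or an abnormal curve. It does not mention Physiocal.

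**2. The plan's own figure.** Inputs from SAP 2.3.1: 60 evaluable subjects needed, "34.5% rejection rate for hemodynamic instability", and 10% loss to follow-up.

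60 / [(1 − 0.345) × (1 − 0.10)] = 60 / 0.5895 = 101.8, rounded up to 102. Adding 6 roll-in subjects gives 108, which reproduces the plan. Conversely, 102 × 0.655 × 0.90 = 60.1 evaluable subjects expected.

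**3. FloTrac subjects if ClearSight-only rejections did not count against FloTrac.** Let *s* be the share of the 34.5% that comes from ClearSight-only signals. The documents do not give *s*, so it is assumed.

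FloTrac evaluable n = 102 × [1 − 0.345 × (1 − *s*)] × 0.90

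**4. Power at those n**, at alpha 0.025 per comparison.

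- Bias: one-sample equivalence t-test (two one-sided tests), true bias 0, SD 1.0 L/min, margin 0.5 L/min (SAP 2.3.1).
- Percent error: one-sided t-test by the noncentral t distribution, SD 70% (SAP 2.3.2), reading the plan's 30% as the difference to be detected.

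| *s* (assumed) | FloTrac evaluable n | Bias power | PE power |
|---|---|---|---|
| 0% | 60.1, about 60 | 93.6% | 90.4% |
| 25% | 68.0, about 68 | 96.5% | 93.6% |
| 50% | 76.0, about 76 | 98.1% | 95.8% |
| 75% | 83.9, about 84 | 99.0% | 97.3% |

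The upper bound, *s* = 100%, gives 102 × 0.90 = 91.8 subjects. The recovery therefore lies between 0 and 31.7 subjects.

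**5. What exclusion could hide, as illustration only.** Suppose 34.5% of pairs are rejected, retained pairs have bias 0 and SD 1, and rejected pairs have bias *d* and SD *k*. Then:

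- all-pairs bias = 0.345 × *d*
- all-pairs variance = 0.655 + 0.345 × *k*² + 0.345 × 0.655 × *d*²

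The bias reaches 0.5 L/min only at *d* = 0.5 / 0.345 = 1.45 L/min. With *d* = 1.5 and *k* = 2, the bias is 0.52 and the SD is √(0.655 + 1.380 + 0.508) = 1.6, while the retained pairs still show 0 and 1.0. Nothing in the documents says what *d* or *k* would be.

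**The case against.** **Stability screening is legitimate.** The protocol's thermodilution section says that variability undermines the stability the technique requires. The MAP and pulse rules therefore protect the reference method and are not performance filters on the test devices. This stands. It does not explain why a value displayed by ClearSight alone should remove a FloTrac pair.

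**A common set of boluses is defensible.** SAP 4 describes one analysis set, and shared boluses keep the two comparisons on the same footing. That is a real advantage. But the study does not test FloTrac against ClearSight; each is tested against Swan-Ganz.

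**Rejection need not lose the subject.** Series can be repeated, and each CO value averages three of four boluses. This is fair, and the table may overstate the recovery. Against it, the Physiocal bullet in SAP 2.2.1 carries no repeat step, SAP 6.3 applies the criteria after data download and foresees missed repeats, and the sample size treats 34.5% as a loss of subjects.

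**FloTrac already has enough power.** At 60 subjects it meets the 90% target for both endpoints, and at *s* = 0% there is nothing to gain. This stands and limits the size of the point.

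**Stronger readings that the documents do not support.**

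- A reader might infer that agreement is judged only when the device under test works well. The confirmatory tests do use non-rejected pairs, but SAP 3.1.2, 3.4.1 and 6.3 plan analyses that include rejected data. What these lack is a decision rule.
- A reader might take Physiocal for a signal-quality index and conclude that the ClearSight results are optimistic. The documents never define it that way and list it under hemodynamic instability.
- A reader might conclude that a MAP swing on the finger cuff alone rejects a bolus. SAP 2.2.1 says that both devices display MAP, not which one triggers rejection. That is an ambiguity, not a stated rule.

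**Conclusion.** The point holds in a limited form. As written, a ClearSight-only signal excludes FloTrac versus Swan-Ganz pairs from the primary and secondary tests, although the two comparisons are tested separately. This rests on the text alone.

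The size cannot be fixed, because the 34.5% is not broken down by rule. Over assumed ClearSight-only shares of 0 to 75%, FloTrac would keep about 60 to 84 of 102 subjects and bias power would run from 93.6% to 99.0%. These figures also rest on a true bias of 0, an SD of 1.0 L/min, and rejection acting at subject level. Neither endpoint depends on the gain; the benefit is better FloTrac precision and exclusions that belong to the comparison they affect.

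The documents do not establish that the ClearSight results are biased by the rule, or by how much. The illustration shows only that rejected pairs would have to differ by about 1.45 L/min before the all-pairs bias reached the margin, whereas the SD could grow with smaller differences. Reporting rejections by rule would settle this with data.

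**What to change.** 1. In SAP 2.2.1 and 6.3, state that in the analysis the Physiocal exclusion applies only to ClearSight versus Swan-Ganz pairs. In SAP 4 and 5.2, define the evaluable set separately for each comparison.
2. Name the signal that governs the MAP and pulse rules when the two devices disagree. The arterial-line signal would stop finger-cuff artefact from removing FloTrac data. It is not independent of FloTrac, however: the FloTrac sensor attaches to the pressure catheter (protocol section 2), and SAP Table 1 lists MAP for FloTrac and ClearSight only. The SAP should say so.
3. Tabulate rejected boluses by rule and by the device whose signal triggered the rejection, with the number of subjects affected in each comparison.
4. Turn the analysis of all recorded values, already planned in SAP 3.1.2, 3.4.1 and 6.3, into a named sensitivity analysis of the primary endpoint for each device, judged against the same ±0.5 L/min margin.

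The cost is SAP wording, one table and one named analysis run per device. No new data are needed, because all values are recorded and rejected ones flagged. The downside is that the two comparisons may rest on different boluses and different n, which the report should show side by side.
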